13.0 Statistical Considerations

This longitudinal study will compare the effects of the three prostheses on the various measured quantities for each subject. Motion capture data will be filtered with an 8 Hz Butterworth low-pass filter, and ground reaction forces will be filtered with a 50 Hz critically damped filter. These data will be collected and analyzed primarily to interpret how differences in kinematics and kinetics associated with the prostheses contribute to corresponding differences in socket pressure and limb health measures. All pressure measurements will be normalized with respect to body weight as measured during the session of data collection. Mean peak pressure within and pressure-time integrals across each gait cycle will be calculated for each sensor location. The peak pressure provides an indication of the maximum loading at any location, while the pressure-time integral combines both the magnitude and duration of loading since both are relevant for limb health.

The 3D scans of the residual limb will be compared between Visits 2 and 4 and between Visits 4 and 6 as a means of interpreting whether significant changes in socket pressure are due to corresponding changes in residual limb volume and/or shape. Both TEWL and skin perfusion, i.e., laser speckle imaging, will be measured or quantified into continuous scales from a three-period, baseline, 30 min post-fitting and 4 weeks post-fitting. The values will be normalized using the values collected from the corresponding reference site [62].

Mean peak socket pressure will serve as the primary outcome measure, with particular emphasis on the proximal region of the anterior surface. Pressure-time integrals will serve as the secondary outcome measure, again emphasizing the same region. TEWL values will be used as the primary outcome measure of overall limb health, while skin perfusion will be the secondary outcome measure. For each measure, comparisons among the three prostheses will be made via a repeated measures ANOVA with Bonferroni correction. For both aims, the survey responses will provide a means of evaluating whether subject impressions aligned with quantitative measures of socket pressure and limb health.

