7.0 Study Procedures

Socket Comfort Score survey: a subjective measure on an 11-point scale of how comfortable the individual feels in the socket. (“On a 0 to 10 scale, if 0 represents the most uncomfortable socket fit you can imagine, and 10 represents the most comfortable socket fit, how would you score the comfort of the socket fit of your artificial limb at the moment?”).

PEQ-13 survey: a 13-question subset of the Prosthesis Evaluation Questionnaire that focuses on the perceived potential for mobility, ambulation, and transfers while using a prosthetic device.

The PEQ-13 uses a 100-point formatted visual analog scale with a scoring range of 0 to 130 in which a higher score indicates high functioning.

CLASS Survey (Comprehensive Lower Limb Amputee Socket Survey): this survey is a self report measure of socket fit that asks the subject to rate stability, comfort, appearance and suspension for their prosthetic socket.

Pressure Sensors (Tekscan F-Socket System): pressure sensors will be placed inside the socket to quantify the amount of force that the participant puts on their residual limb. The sensors will be trimmed to fit the curvature of the socket interface so that reliable measurements can be made in the distal, medial, and proximal regions on the anterior and posterior surfaces of the socket, as well as the fibular head.

Shape Capture: The experimenter will conduct a 3D scan of the residual limb to capture its shape using an optical tracking CAD/CAM system.

K3 Activity Level: Has the ability or potential for ambulation with variable cadence, typical of the community ambulator who has the ability to transverse most environmental barriers and may have vocational, therapeutic, or exercise activity that demands prosthetic utilization beyond simple locomotion.

TEWL: Transepidermal water loss quantifies the functional integrity of the skin. A breach in the physical integrity of the skin (i.e. ulceration) is preceded by breach of functional integrity of the skin, which is indicated by elevated TEWL measurements. This instrument is a non-invasive probe that is placed on the skin that measures water loss coming from the skin. The PI's prior work has shown that, like socket pressure, TEWL is affected by the type of suspension.

Weight: We will obtain weight at all study visits

Laser Speckle Imaging (LSI): A non-invasive device that measures blood flow, referring to the rate of blood flow through the vessels serving the skin.

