14.0 Statistical Data Management

14.1 CLINICAL DATA: Will be recorded in RedCap (research electronic data capture (HIPAA compliant) as clinical research database. Prior to being given access to the data, HIPAA and human subjects certified “study staff” will be trained in the collection of patient-reported outcomes. Study data will be collected using standardized case report forms (CRFs), with clear, uniform instructions for study staff. Researcher’s access to files will be governed by institutional secure data access policies. The RedCap platform is developed and operated by IU clinical research IT team.

14.2 DATA QUALITY AND SECURITY. The study team will review all CRFs. All incoming data will be monitored, with particular attention to: 1) enrollment and follow-up reports as entered into the database; 2) potential adverse events, and 3) missing data or extreme values. The clinical database administrator will generate reports of enrollment progress and data quality control results, to be distributed to the study team bi-monthly and ad hoc as needed, as well as to the safety committee.

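### The plan describes no masking of the foot when pressure and laser-speckle recordings are reduced to outcomes; coding each recording would cheaply reduce any selective processing.

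*Combined protocol and SAP*

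**What the plan says.** Section 13.0 defines the pressure outcomes: "Mean peak pressure within and pressure-time integrals across each gait cycle will be calculated for each sensor location". Mean peak pressure is primary, "with particular emphasis on the proximal region of the anterior surface". Section 7.0 says the sensors are trimmed to the socket so that "reliable measurements can be made in the distal, medial, and proximal regions on the anterior and posterior surfaces of the socket", and at the fibular head.

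For limb health, Section 13.0 says "Both TEWL and skin perfusion, i.e., laser speckle imaging, will be measured or quantified into continuous scales", and adds that "The values will be normalized using the values collected from the corresponding reference site". Signal processing is fixed for other data streams ("Motion capture data will be filtered with an 8 Hz Butterworth low-pass filter", and a separate filter for ground reaction forces), but no filter is given for socket pressure and no processing step for speckle images.

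Section 14.2 has the study team review the case report forms and lists "missing data or extreme values" among the items to be watched. Section 15.2 provides a subject code for material going to analysis, which research nurses and investigators can link to identity. The available text does not mention blinding, masking or a masked reader.

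**The concern.** The feet cannot realistically be hidden at the visits: a prosthetist fits them, and trials are run with the battery on and off. Reducing the recordings to outcome values comes afterwards, and it is the one stage where masking is practical. It also involves judgement. Someone who knows the foot and decides whether a cycle is faulty, where the proximal anterior region ends on a trimmed sensor, or where to draw the speckle region could decide differently for different feet without intending to.

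The primary pressure outcome and the perfusion outcome both pass through such decisions. A consistent lean toward one device does not average out over subjects. It would enter the comparison of feet as if it were a device effect, and the repeated measures ANOVA could not tell the two apart.

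**Working it through.** **What is fixed and what is open**

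| Step | Fixed in the plan | Left open |
|---|---|---|
| Gait cycles | Metrics computed for each cycle (13.0) | What makes a cycle valid; how many are used |
| Pressure regions | Regions listed (7.0); proximal anterior emphasised (13.0) | Boundaries on the trimmed sensor; emphasis does not fix a single test region |
| Pressure scaling | Body weight from the same session (13.0) | Filter or artefact rule |
| Laser speckle | Normalised to a reference site (13.0) | Region of interest, frame selection, reader |
| Extreme values | Monitored (14.2) | Whether any are excluded, and by what rule |
| Coding | Subject code for privacy (15.2) | Nothing hides the foot |

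**Illustrative size**

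The plan states no sample size, alpha, SD or power, so it has no figure to reproduce. Section 11.0 schedules a safety review after the 10th enrolment, which suggests at least 10 subjects. All inputs below are assumptions: N = 12 or 20; two-sided alpha of 0.05, or 0.05/3 for three Bonferroni comparisons; and a lean *b* of 0.1, 0.2 or 0.3 SD of the paired difference. A paired t test stands in for one pairwise comparison within the ANOVA.

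With no true device effect, the test statistic follows a noncentral t distribution with N − 1 degrees of freedom and noncentrality b√N. The false-positive rate is P(T > c) + P(T < −c), where c is the usual critical value. For example, with N = 12 and b = 0.3, noncentrality is 0.3 × √12 = 1.04, c = 2.201 and the rate is 15.8%. With N = 20 and b = 0.3, noncentrality is 0.3 × √20 = 1.34, c = 2.093 and the rate is 24.7%.

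| N | Nominal rate | b = 0.1 | b = 0.2 | b = 0.3 |
|---|---|---|---|---|
| 12 | 5% | 6.2% | 9.7% | 15.8% |
| 12 | 1.7% | 2.2% | 3.8% | 7.0% |
| 20 | 5% | 7.1% | 13.6% | 24.7% |
| 20 | 1.7% | 2.6% | 5.9% | 12.5% |

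**How large a lean could one choice produce?**

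Suppose each foot gives 10 cycles (assumed) and the highest is dropped for one foot only. The expected maximum of 10 standard normal values is 1.54, so the mean of the remaining nine falls by 1.54/9 = 0.171 cycle SDs. If the cycle SD is 0.25, 0.5 or 1.0 times the between-subject SD of the paired difference, the lean is 0.04, 0.09 or 0.17 of that SD. In simulation (20,000 trials per setting, N = 10 to 20), a nominal 1.7% rate became 1.7-1.8%, 1.9-2.5% or 2.6-4.0%. One such choice can therefore be harmless or modest in effect. It does not reach 0.2 SD, and 0.3 SD would need more than this.

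**Which recordings a code can mask**

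The study calendar places laser speckle at Visits 1, 3 and 5, with one foot in use at each. Pressure sessions mix conditions: Visit 2 has the standard foot and Foot A; Visit 4 has Foot A with battery on and off, then Foot B; Visit 6 has Foot B with battery on and off. A code per session would leave the feet distinguishable within a pressure session. The standard foot is recorded under pressure only at Visit 2, so the visit label alone helps to identify it.

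**The case against.** Much of the case on the other side stands.

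- A reader might infer that an open-label study team processes the files. The documents do not say so: the processor is not named and that term is not used. They support only that no masked processing is described. The front matter was not available for this review, so a statement there cannot be ruled out.
- A reader might take Section 14.2 as letting the team act on extreme values knowing the foot. The sentence beginning "All incoming data will be monitored, with particular attention to: 1) enrollment and follow-up reports as entered into the database" concerns database quality control. It does not mention raw pressure files or speckle images and contains no exclusion rule in either direction.
- Computing the metrics for each cycle and each location can be read as using all of them, and the regions are named in advance. That narrows the discretion over pressure to cycle validity and boundaries; for speckle images the region remains open.
- The reference site is part of taking the measurement, so file coding cannot protect it.
- It is tempting to say that a small sample makes the problem worse. The table shows the reverse: a fixed lean inflates the error rate more as N grows.
- The instruments are objective, and the error rates above rest wholly on assumptions.

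None of this supplies masking or rules for the steps that remain open.

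**Conclusion.** The gap holds in a limited form, as a cheap improvement and not as evidence of bias. The available text keeps knowledge of the foot away from no processing step, and the privacy code does not do that job. Discretion remains over cycle validity, region boundaries and the speckle region of interest. The size of any lean cannot be derived from the documents and may be negligible; the tabulated rates show only what follows if a lean of 0.1 to 0.3 SD existed. The stronger claim that coded files would prevent the bias is not supported. Coding leaves acquisition unmasked, including sensor placement and choice of the reference site, and a powered foot may be recognisable from its trace.

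**What to change.** Add to Section 13.0:

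- Save each pressure trial recording (one per foot, battery state and task, not one per session) and each laser-speckle image under a random code, with foot, visit and battery state removed.
- Have the key held by an existing staff member who does not process the files.
- Before processing starts, write the rules for valid cycles, region boundaries, the speckle region of interest and any exclusions, and apply them under the code.
- Lock the derived values before the foot labels are merged for the ANOVA.

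No visit, procedure or participant burden is added. The cost is splitting and relabelling recordings from mixed sessions, which is more than renaming session files, plus a short delay before labelled results can be seen. The documents give no staffing figures, so the low cost is a judgement.

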The most common quantitative measure of prosthetic fit is pressure inside the socket during locomotion activities, and a wide range of measurement techniques have been pursued [41, 42]. Results show that mediolateral pressures tend to be less than anterior and posterior pressures, with anterior pressures typically being the highest [43]. Walking on slopes and stairs is of particular interest since internal stresses are known to be elevated in these cases [44] and pressure in level-ground walking is a poor predictor of that in these more challenging circumstances [45]. In stair ascent, the highest pressures are located in the proximal region of the anterior surface [46, 47], whereas they shift to the distal region with stair descent [47]. Gait and Motion Analysis is of particular interest to understand how a participant's gait can affect the amount of pressure that they place on their residual and intact limb. Beyond these activity-specific results, socket pressure has also been shown to be influenced by the type of suspension [43, 46], the type of foot [48, 49], and the alignment of the prosthesis [50–54].

Measuring fit via socket pressure, though, remains one step removed from limb health, the actual quantity of interest. More direct measures of limb health include transepidermal water loss (TEWL) for quantifying the functional integrity of the skin and laser speckle imaging (LSI) for quantifying skin perfusion. The PI's prior work has shown that, like socket pressure, TEWL is affected by the type of suspension (Fig. 3), but perfusion is not necessarily (Fig. 4) [62]. No studies to date have examined the effects of active lower-limb prostheses, neither micro-controlled nor powered, on these direct measures of limb health.

Active prostheses like the PROPRIO FOOT® and Empower ankle offer great potential to more completely restore the locomotor capabilities of individuals with transtibial amputation, perhaps enhancing RTD for military personnel. As with all prosthetic components, though, these active devices are of little use if they induce pain and/or injury at the residual limb to the degree that the user will simply not wear them. Overall, this project seeks to understand and quantify the effects of powered transtibial prostheses on socket loading and direct measures of residual limb health so as to inform the optimization of prosthesis fit.

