2.0 Objective(s)

2.1 Primary Objective

Use of the powered Empower ankle prosthesis to determine differences in socket pressures compared to both the microprocessor-controlled PROPRIO FOOT® and a user's standard passive prosthesis for level-ground walking, stair ascent, and ramp ascent.

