3.0 Outcome Measures/Endpoints

3.1 Primary Outcome Measures

Determine the effects of a powered transtibial prosthesis on the socket pressure for level-ground walking, stair ascent/descent, and ramp ascent/descent in comparison to a microprocessor-controlled prosthesis and a passive prosthesis at 4 weeks.

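### The primary socket-pressure tests are not fixed: 2.1 and 3.1 list different tasks, the anterior-proximal region is only emphasised, and nothing says how tasks enter the multiplicity correction

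*Combined protocol and SAP*

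**What the plan says.** **Tasks.** Section 2.1 compares the Empower ankle with the PROPRIO FOOT and the user's "standard passive prosthesis for level-ground walking, stair ascent, and ramp ascent". Section 3.1 defines the primary outcome "for level-ground walking, stair ascent/descent, and ramp ascent/descent in comparison to a microprocessor-controlled prosthesis and a passive prosthesis at 4 weeks". The first list has three tasks; the second has five, adding stair descent and ramp descent.

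**Region.** Section 13.0: "Mean peak socket pressure will serve as the primary outcome measure, with particular emphasis on the proximal region of the anterior surface". The same section says "Mean peak pressure within and pressure-time integrals across each gait cycle will be calculated for each sensor location". Section 7.0 places sensors in the "distal, medial, and proximal regions on the anterior and posterior surfaces of the socket, as well as the fibular head", which counts to seven locations (3 + 3 + 1); the documents give no total.

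**Test.** Section 13.0: "For each measure, comparisons among the three prostheses will be made via a repeated measures ANOVA with Bonferroni correction". No section states an alpha, the role of task in the model, or whether pairs are tested only after a significant ANOVA.

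**Recordings.** Under 5.0, the passive foot's pressure is recorded only at Visit 2. Each active foot is recorded after 15-30 minutes of acclimation (Visits 2 and 4). After the wear period (Visits 4 and 6, or the combined visits) it is recorded again, with battery on and with battery off. At Visit 6 the passive foot is refitted with no further trials.

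**The concern.** A reader cannot tell from the plan which tests decide the primary question. The task list, the standing of the emphasised region and the scope of the correction could all still be settled after the data are seen.

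The background section gives hints that 13.0 does not turn into rules. It says that "pressure in level-ground walking is a poor predictor of that in these more challenging circumstances", which argues against quietly pooling tasks. It says that in stair ascent "the highest pressures are located in the proximal region of the anterior surface", which supports the emphasised region for that task. It also reports that the peak moves distally in stair descent, which fits poorly with adding stair descent while emphasising a proximal region.

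If tasks are tested one by one and the correction covers devices only, the chance of at least one false primary finding rises above 5%. If tasks are averaged, that chance is controlled, but 2.1's question about each task goes unanswered.

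**Working it through.** The plan states no error rate, power or sample size, so there is no figure of its own to reproduce.

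**Inputs from the documents:** 3 prostheses, hence 3 pairs; 3 tasks (2.1) or 5 tasks (3.1); one emphasised region (13.0).

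**Assumed:** alpha 0.05 two-sided; N = 10 to 20 (11.0 plans a review after the 10th subject, and the upper end is a choice); normal, spherical errors; equal between-task correlation of 0, 0.5 or 0.8; no true differences.

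**Step 1, simple reference.** Bonferroni over 3 pairs tests each at 0.05/3 = 0.0167, so each task has error of at most 5%. If tasks were independent and each used the full 5%:
- 3 tasks: 1 − 0.95³ = 14.3%
- 5 tasks: 1 − 0.95⁵ = 22.6%

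**Step 2, simulation allowing for correlation.** Family-wise error in the emphasised region at N=12, with the range over N = 10 to 20 and all correlations:

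| Reading | Tasks | Corr. 0 | 0.5 | 0.8 | Range |
|---|---|---|---|---|---|
| Separate tasks, Bonferroni over 3 pairs | 3 | 12.9% | 12.2% | 9.9% | about 9-13% |
| Same | 5 | 20.7% | 18.3% | 13.0% | about 12-21% |
| Separate tasks, ANOVA significant, then Bonferroni pairs | 3 | 9.1% | 8.6% | 6.9% | about 6-10% |
| Same | 5 | 14.8% | 13.0% | 9.2% | about 9-16% |

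Readings that control error, over the same grid:
- Tasks averaged into one device test: 4.5-5.3% for the ANOVA, 4.1-4.9% for Bonferroni pairs, 2.9-3.6% if both are required.
- Bonferroni over all pairs and tasks (9 or 15 tests): about 3-5%.

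**Step 3, price of a full correction.** Holm's first step is 0.05/k for k tests. Worst-case power for a single contrast is the power of a paired t-test at that level, from the noncentral t with N−1 degrees of freedom and noncentrality d√N. For an assumed d = 1.0, the noncentrality is 3.46 at N=12 and 4.47 at N=20:

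| Tests k | Composition | First step | N=12 | N=20 |
|---|---|---|---|---|
| 3 | 3 pairs, devices only | 0.0167 | 73% | 96% |
| 6 | 2 contrasts × 3 tasks | 0.0083 | 61% | 92% |
| 9 | 3 contrasts × 3 tasks | 0.0056 | 54% | 89% |
| 10 | 2 contrasts × 5 tasks | 0.0050 | 52% | 88% |

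At d = 0.8, moving from 3 to 6 tests lowers power from 51% to 38% (N=12) or from 82% to 73% (N=20). Family-wise error under Holm is about 3.5-4.9% with 6 tests and 3.2-4.9% with 10.

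**The case against.** Section 13.0 never says outright what Bonferroni covers. A team that extended it to tasks, or averaged tasks, would keep error at about 5% or below, and both are plausible readings. The study states no success rule; it sets out to describe differences among devices. Every percentage above rests on an assumed alpha, N and correlation.

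All of this is right, and it limits the point. A reader might infer that the plan as written has inflated error. The documents do not support that: inflation follows only if tasks are tested separately with correction over devices alone.

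A reader might also count all seven locations by five tasks as co-primary and arrive at a far larger error. That gives no weight to the stated emphasis on one region.

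Nor does the four-week wording in 3.1 make the comparison with the passive foot invalid. Participants enter already using a passive prosthesis (4.1), so the phrase can be read as wear time on the research feet. It still needs rewording, because the passive foot has no four-week recording.

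What remains is that 2.1 and 3.1 disagree on the primary tasks, and no section says how tasks are analysed or corrected. Neither depends on the assumed figures.

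**Conclusion.** The point holds as a gap in the definition of the primary analysis, and it should be closed before the data are analysed. The conflict between three and five tasks is a contradiction in current text; the status of the region and the handling of tasks are left open.

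Depending on the reading, family-wise error in the emphasised region runs from about 3% to about 21% under the stated assumptions. That spread shows how much the open choices matter; it does not estimate the trial's actual error rate. The choice of region for level walking and ramp ascent rests on 13.0's emphasis, since the background locates the peak there for stair ascent only.

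**What to change.** - **Tasks:** make 2.1 and 3.1 list the same tasks. Use the three in 2.1, or change 2.1 if the descents are to stay primary.
- **Endpoint:** name body-weight-normalised mean peak pressure in the anterior-proximal region as the single primary endpoint. Make other locations, pressure-time integrals, battery-off recordings and recordings after 15-30 minutes of acclimation secondary or exploratory.
- **Recordings:** state that the comparison uses the battery-on recordings after the wear period for the two active feet (Visits 4 and 6, or the combined visits) and the Visit 2 recording for the passive foot. Reword 3.1's time point to match.
- **Testing:** state alpha, analyse each task separately, and apply Holm over all primary contrasts by tasks. Holm is never less powerful than Bonferroni over the same tests. With three tasks this is 9 tests if all three device pairs stay primary, or 6 if the team limits the primary contrasts to the two that 2.1 and 3.1 name (Empower against PROPRIO FOOT, Empower against passive). That limit is the team's choice; closing the gap does not require it.

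**Cost:** wording only, with no new data. Worst-case power for a single contrast falls: with 6 tests and a paired effect of 1.0, from 73% to 61% at N=12 and from 96% to 92% at N=20, and further with 9 tests. Some results become exploratory. The passive foot is still always recorded first, so its comparisons remain unbalanced for order; this fix does not change that.
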